3.1.7 Prior and concomitant medications

Medications taken by any subject at any time during the study will be coded using the ATC classification system within the WHO Drug Dictionary.

Medications will be categorised for analysis according to their onset and end dates as follows, where first dose of IP refers to first dose of IP in the predecessor studies:

- Prior medications:
 - end date < date of first dose of IP
- Concomitant medications during on-treatment period:
 - end date > date of first dose of IP in the predecessor study and start date \le minimum (date of last dose of IP + 33 days, date of death, date of study withdrawal), or
 - end date ongoing and start date ≤ minimum (date of last dose of IP + 33 days, date of death, date of study withdrawal)
- Concomitant medications during post-treatment period:
 - start date > date of last dose of IP + 33 days.

Essentially the above says that:

- Prior and concomitant medications are mutually exclusive.
- Concomitant medications on-treatment and post-treatment are also mutually exclusive (here, the word "concomitant" means concomitant with study procedures, irrespective of whether IP was still being taken). Specifically, a concomitant medication which started on-treatment and ended post-treatment will only be considered on-treatment.

In addition, concomitant medications will be categorised by predecessor period and LTE period as follows:

- Concomitant medications during on-treatment predecessor period:
 - end date > date of first dose of IP in the predecessor study and start date ≤ minimum (date of last dose of IP in the predecessor study + 33 days, date of death, date of study withdrawal, date of enrolment into the LTE study*), or

- end date ongoing and start date ≤ minimum (date of last dose of IP in the predecessor study + 33 days, date of death, date of study withdrawal, date of enrolment into the LTE study*)
- Concomitant medications during on-treatment LTE period:
 - end date > date of enrolment in the LTE study* and start date ≤ minimum (date of last dose of IP in the LTE study + 33 days, date of death, date of study withdrawal), or
 - end date ongoing and start date ≤ minimum (date of last dose of IP in the LTE study
 + 33 days, date of death, date of study withdrawal)

If the medication record has a completely missing onset date, the subject will be assumed to have been on the medication on the date of the first study procedure. If the medication record has a partially missing onset date (month/year or year only) which is the same as that for the end of IP treatment, it will be assumed to have started on-treatment. If the medication record has a partially missing onset date (month/year or year only) which is the same as that for the start of IP treatment, it will be assumed to have started before treatment.

If the medication record has a completely missing end date, the subject will be assumed to have been on the medication on the date of study completion or withdrawal. If the medication record has a partially missing end date (month/year or year only) which is the same as that for start of IP treatment, it will be assumed to have ended on-treatment. If the medication record has a partially missing end date (month/year or year only) which is the same as that for end of IP treatment, it will be assumed to have ended post-treatment.

3.1.8 Definition of subgroups

The following subgroups are defined for the purposes of efficacy and safety subgroup analyses and/or demographic and baseline summaries where baseline will be defined as specified in Section 3.1.2. Efficacy and safety subgroup analyses will only be conducted on summary data from subjects with D5180C00007 as predecessor study; variables to be analysed by subgroup are marked with *. If any of the subgroups has fewer than 10 subjects in one or both treatment arms, the corresponding safety and efficacy subgroup analyses will not be conducted.

For D5180C00007:

- *Baseline eosinophils group: $<300/\mu L$, $\ge 300/\mu L$
- Baseline eosinophils group: $<150/\mu$ L, $150-<300/\mu$ L, $300-<450/\mu$ L, $\ge450/\mu$ L
- *Baseline eosinophils group: $<150/\mu L$, $\ge 150/\mu L$ (only for analyses of AAER)

^{*} For subjects in the Placebo Predecessor+Tezepelumab LTE treatment group who do not receive their first dose of IP in the LTE study on the date of enrolment into the LTE study, replace the date of enrolment into the LTE study with the date of first dose of IP in the LTE study in the derivations above.

- *Baseline clinic visit FeNO group: <25ppb, ≥25ppb
- Baseline clinic visit FeNO group: <25ppb, 25-<50ppb, ≥50ppb
- Baseline (Any) specific IgE status (FEIA): Any FEIA positive, All FEIA negative, Unknown FEIA
 - "Any FEIA positive" requires 1 or more specific IgE panels using fluorescent enzyme immunoassay (FEIA) to be positive. Provided that at least one IgE panel is positive, no further requirement is made for data on all 12 panels to be available.
 - "All FEIA negative" requires all 12 specific IgE panels to be negative. If there are fewer than 12 panels with data available and none of these is positive, then IgE status is considered "Unknown FEIA".
 - Positive is defined as a value ≥ 0.35 kU/mL.
- * Baseline perennial specific IgE status (FEIA): Any perennial FEIA positive, All perennial FEIA negative, Unknown perennial FEIA
 - "Any perennial FEIA positive" requires 1 or more specific IgE (FEIA) panels to be positive. Provided that at least one IgE panel is positive, no further requirement is made for data on all 8 panels to be available.
 - "All perennial FEIA negative" requires all 8 specific IgE panels to be negative. If there are fewer than 8 panels with data available and none of these is positive, then IgE status is considered "Unknown perennial FEIA".
 - Positive is defined as a value ≥0.35 kU/L. The 8 panels include: American Cockroach, Cat Dander, D. farina, D. pteronyssinus, Dog Dander, German Cockroach, Mould Mix, Oriental Cockroach.
- Baseline seasonal specific IgE status (FEIA): Any seasonal FEIA positive, All seasonal FEIA negative, Unknown seasonal FEIA
 - "Any seasonal FEIA positive" requires 1 or more specific IgE (FEIA) panels to be positive. Provided that at least one IgE panel is positive, no further requirement is made for data on all 4 panels to be available.
 - "All seasonal FEIA negative" requires all 4 specific IgE panels to be negative. If there are fewer than 4 panels with data available and none of these is positive, then IgE status is considered "Unknown seasonal FEIA".
 - Positive is defined as a value ≥0.35 kU/L. The 4 panels include: Grass Mix Pollen,
 Silver Birch Pollen, Weed Mix Pollen, Japanese Cedar.
- *ICS dose at study entry: low, medium, high (as defined in Appendix 8.3 only for analyses of AAER)
- *OCS at baseline: present, absent. Note OCS at baseline will be defined as OCS administered at baseline for disease under study (only for analyses of AAER)
- Age category used for stratification: adults (≥ 18) and adolescents (≥ 12 to < 18)
- *Age category: adults (\geq 65), adults (\geq 18 to <65) and adolescents (\geq 12 to <18)
- Gender: Male, Female
- Race: White, Black or African American, Asian, Other
- *Exacerbations in the year before study: \(\le 2 \) exacerbations, \(> 2 \) exacerbations

- Baseline body mass index (BMI): $<18.5 \text{ kg/m}^2$, $18.5 <25.0 \text{ kg/m}^2$, $25.0 <30.0 \text{ kg/m}^2$, $\ge 30.0 \text{ kg/m}^2$
- Geographical region: Asia Pacific [incl. Japan, South Korea, Taiwan and Vietnam], North America [incl. Canada and USA], South America [incl. Argentina and Brazil], Central/Eastern Europe [incl. Russia and Ukraine], Western Europe plus Australia [incl. Austria, France, Germany, UK and Australia], Rest of World [incl. Israel, Saudi Arabia and South Africa]. Note all subjects from Japan who were in study C00007 were not enrolled into the LTE study.
- Country
- Baseline CRSwNP status: Yes, No
 - Chronic rhinosinusitis with nasal polyps at baseline will be defined by the presence
 of the following on the Respiratory Disease History eCRF page for a particular
 subject: Nasal polyps plus at least one of (Diagnosis of rhinitis; Diagnosis of chronic
 sinusitis).
- Nasal polyps status at study entry: Yes, No
 - Nasal polyps at baseline will be defined by the presence of nasal polyps on the Respiratory Disease History eCRF page for a particular subject.
- *Nasal polyps in the 2 years before randomisation status: Yes, No

Nasal polyps in the 2 years before randomisation will be defined by the presence of nasal polyps on the Respiratory Disease History eCRF page for a particular subject, with no associated stop date on the Medical History eCRF or an associated stop date less than, or equal to 24 months before randomisation.

For D5180C00009:

- Baseline eosinophils group: $<300/\mu L$, $\ge 300/\mu L$
- Baseline eosinophils group: <150/μL, ≥150/μL
- Baseline eosinophils group: $<150/\mu L$, $\ge 150/\mu L$ to $<300/\mu L$, $\ge 300/\mu L$ to $<450/\mu L$, $\ge 450/\mu L$
- Baseline clinic visit FeNO group: $< 25ppb, \ge 25ppb$
- Baseline clinic visit FeNO group: <25ppb, 25-<50ppb, ≥50ppb
- Baseline (Any) specific IgE status (FEIA): defined the same as D5180C00007
- Baseline perennial specific IgE status (FEIA): defined the same as D5180C00007
- Baseline seasonal specific IgE status (FEIA): defined the same as D5180C00007
- OCS dose at randomisation: (≤10 mg versus >10 mg prednisone or prednisolone)
- Age category: adults (\geq 65) and adults (\geq 18 to <65)
- Gender: Male/Female
- Race: White, Black or African American, Asian, Other
- Baseline body mass index (BMI): $<18.5 \text{ kg/m}^2$, $18.5 <25.0 \text{ kg/m}^2$, $25.0 <30.0 \text{ kg/m}^2$, $>=30.0 \text{ kg/m}^2$

- Geographical region: Western Europe and North America (incl. Germany and USA);
 Central/Eastern Europe (incl. Poland, Turkey and Ukraine); Rest of World (incl. Argentina and South Korea).
- Country

3.1.9 Disposition

The following definitions will be used for time to event variables in Kaplan-Meier disposition plots:

Time to last dose of IP

Time to last dose of IP will be defined as follows:

Time to last dose (days) = [Date of last dose of IP from eCRF – date of first dose of IP in the predecessor studies] + 1.

Date of last dose of IP will be the date of last dose taken from the "Discontinuation of Investigational Product" eCRF page for all subjects; those who prematurely discontinue IP as well as those who complete IP dosing as per protocol. For subjects who are not enrolled in the LTE study or do not receive IP during the LTE study, the date of last dose of IP will be taken from the predecessor study eCRF.

Subjects on placebo in a predecessor study, enrolled in LTE study, and randomised to receive tezepelumab in the LTE study will be censored on the date of last dose of IP taken from the predecessor study eCRF.

Time to premature study withdrawal

Time to premature study withdrawal will be defined as follows:

Time to premature study withdrawal (days) = [study withdrawal date from eCRF - date of randomisation in the predecessor studies] + 1.

Study withdrawal date will be the completion or discontinuation date from the "Disposition" eCRF page, where any subject status other than "Completed" has been entered. For subjects enrolling into the LTE study, this will be the Disposition eCRF from the LTE study (as all subjects enrolling in the LTE study will have completed the predecessor study).

Subjects who did not prematurely withdraw from study will be censored at one of the following dates:

• For subjects not enrolling into the LTE study, completion or discontinuation date from the "Disposition" eCRF page from the predecessor study, where subject status of "Completed" has been entered.

 For subjects enrolling into the LTE study, completion or discontinuation date from the "Disposition" eCRF page from the LTE study, where subject status of "Completed" has been entered.

At primary DBL, ongoing subjects will be censored at their last contact date.

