### **Methods for assigning treatment groups**

All subjects will be centrally assigned to randomized study treatment using an interactive response technology (IRT). Randomization codes will be assigned strictly sequentially in each stratum as subjects become eligible for randomization. Randomization will be stratified by predecessor study.

All subjects will be re-randomized in this study, and will be assigned to treatment according to the following algorithm:

- \* Subjects previously randomized with blinded tezepelumab will be assigned and stay on blinded tezepelumab
- \* Subjects previously randomized to blinded placebo will be randomized 1:1 to blinded

Tezepelumab - D5180C00018  
tezepelumab or placebo.

The randomization list will be prepared by a computerized system provided by Calyx Clinical Research Solutions on behalf of AstraZeneca (AZRand).

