**Figure 4 Treatment Groupings**

**Note:** Groups 2 and 5 reflect subjects in the predecessor studies who do not enrol in the LTE study.

The following treatment groups for analyses will be considered, where time from first dose is applicable for the safety analysis, and time from randomization is applicable for the efficacy analysis:

Primary:

- **Randomized Tezepelumab:** All subjects originally randomized to tezepelumab in the predecessor studies. Will include all data from first dose/randomization in the predecessor studies to end of the LTE study. (A, B and C above).
- **Randomized Placebo:** All subjects originally randomized to placebo in the predecessor studies. Will include all data from first dose/randomization in

Tezepelumab - D5180C00018

predecessor studies up until switch to tezepelumab, and all data from first dose/randomization in the predecessor studies to end of the LTE study for subjects randomized to placebo in the predecessor studies and the LTE study. (D, F, G and H above).

Supportive:

- **Tezepelumab Predecessor+Tezepelumab LTE:** All subjects originally randomized to tezepelumab in the predecessor studies and re-randomized to tezepelumab in the LTE study. Will include all data from first dose/randomization in the predecessor study to end of the LTE study for only subjects enrolled into the LTE study. (A and B above).
- **Placebo Predecessor+Placebo LTE:** All subjects randomized to placebo in the predecessor studies, and later re-randomized to placebo in the LTE study. Will include all data from first dose in predecessor studies until end of the LTE study for only subjects enrolled into the LTE study. (F and G above).

Supportive (for exposure summaries and rare events):

- **All Tezepelumab:** All subjects randomized to tezepelumab in the predecessor studies and subjects randomized to tezepelumab in the LTE study. It will include all data from time of first dose/randomization to tezepelumab. (A, B, C and E above).

Additional (for the assessment of durability of benefit):

- **Tezepelumab Predecessor+Tezepelumab LTE:** as defined above.
- **Placebo Predecessor+Placebo LTE:** as defined above.
- **Placebo Predecessor+Tezepelumab LTE:** All subjects originally randomized to placebo in the predecessor studies and re-randomized to tezepelumab in the LTE study. Will include all data from first dose/randomization in the predecessor studies to end of the LTE study for only subjects enrolled into the LTE study. (D and E above).

CCI

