2.1.2 Treatment groups

There are 5 possible groupings across the predecessor and LTE studies as shown in Figure 2 below.

Figure 2 Treatment groupings

[figure not shown]

Note: Groups 2 and 5 reflect subjects in the predecessor studies who do not enrol in the LTE study.

The following treatment groups for analyses will be considered, where time from first dose is applicable for the safety analysis, and time from randomisation is applicable for the efficacy analysis:

Primary (based on the SAF and FAS analysis sets):

[figure not shown]
- Randomised Tezepelumab (Rand Teze): All subjects originally randomised to tezepelumab in the predecessor studies. Will include all data from first dose/randomisation in the predecessor studies to end of the LTE study. (A, B and C)
- Randomised Placebo (Rand Pbo): All subjects originally randomised to placebo in the predecessor studies. Will include all data from first dose/randomisation in predecessor studies up until switch to tezepelumab, and all data from first dose/randomisation in the predecessor studies to end of the LTE study for subjects randomised to placebo in the predecessor studies and the LTE study. (D, F, G and H)

Supportive (based on the SAF-LTE and FAS-LTE analysis sets):

[figure not shown]
- Tezepelumab Predecessor+Tezepelumab LTE (Teze+Teze): All subjects originally randomised to tezepelumab in the predecessor studies and re-randomised to tezepelumab in the LTE study. Will include all data from first dose/randomisation in the predecessor study to end of the LTE study for only subjects enrolled into the LTE study. (A and B)
- Placebo Predecessor+Placebo LTE (Pbo+Pbo): All subjects randomised to placebo in the predecessor studies, and later re-randomised to placebo in the LTE study. Will

include all data from first dose in predecessor studies until end of the LTE study for only subjects enrolled into the LTE study. (F and G)

[figure not shown]
Supportive (for exposure summaries and rare events based on the SAF analysis set):

[figure not shown]
• All Tezepelumab (All Teze): All subjects randomised to tezepelumab in the predecessor studies and subjects randomised to tezepelumab in the LTE study. It will include all data from time of first dose/randomisation to tezepelumab. (A, B, C and E)

Additional (for the assessment of durability of benefit based on the SAF-LTE and FAS-LTE analysis sets):

- Tezepelumab Predecessor+Tezepelumab LTE (Teze+Teze): as defined above

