4.2 Subject disposition, demography and baseline characteristics

Subject disposition will be summarised using the SAF analysis set for the predecessor period and using the LTE analysis set for the LTE period.

For the predecessor period, the number and percentage of subjects within each treatment group (Randomised Tezepelumab and Randomised Placebo) will be presented by the following categories; received IP, did not receive IP (and reason), completed treatment, discontinued treatment (and reason), completed study (including subjects who completed IP and study, and subjects who discontinued IP but completed study assessments), discontinued study (including reason), and subjects who did not enrol into the LTE study.

For the LTE period, the number of subjects enrolled into the LTE study will be summarised, and the number and percentage of subjects within each treatment group (Tezepelumab Predecessor+Tezepelumab LTE, Placebo Predecessor+Placebo LTE and Placebo Predecessor+Tezepelumab LTE) will be presented by the following categories; randomised, not randomised (and reason), received IP, did not receive IP (and reason), completed treatment, discontinued treatment (and reason), completed study (including subjects who completed IP and study, and subjects who discontinued IP but completed study assessments), discontinued study (including reason), and subjects who enrolled into LTE but had a delay due to COVID-19. Randomisation information will also be listed.

The number and percentage of subjects who discontinued IP, but remained in the study, will be presented by treatment group and option of follow up (Section 1.2) for the SAF-LTE analysis set for the LTE period only. Subject disposition will also be presented in listings. A separate listing will be produced for: those who discontinue IP, those who discontinue the study, and those who complete the study.

Kaplan-Meier plots will be produced summarising separately the time (in days) to last dose of IP and premature withdrawal from the study for the SAF analysis set. Subjects without the premature event will be censored as described in Section 3.1.9. The number of subjects discontinuing IP and prematurely withdrawing from the study will be monitored as the study

progresses. Additional summaries of this data including investigation of the reasons for discontinuations by treatment group may also be provided.

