8.4 Summary of data to be presented

Table 9 Disposition, demographics and baseline characteristics

| Analysis sets | | SAF | | SAF-I | LTE | LTE | CCI |
|---|--|--------------------------|------------|-------------------------|------------|--------------------------------------|-----|
| | Treatment groups | (Rand Teze/ Rand Pbo) | (All Teze) | (Teze+Teze/ Pbo+Pbo) | (Pbo+Teze) | (Teze+Teze/ Pbo+Pbo/ Pbo+Teze) | |
| Study | Data | Overall | Overall | Overall | Overall | Overall | |
| Disposition, demographics and baseline characteristics (Section 4.2, 4.7.1) | | | | | | | |
| Both | Disposition | √ PreD | | | | ✓ LTE | |
| Both | Demographics | ✓ | ✓ | ✓ | ✓ | | |
| C00007 | Demographics by age group $(\ge 12 \text{ to } < 18, \ge 18 \text{ to } < 65, \ge 65)$ | | | ✓ | ✓ | | |
| Both | Baseline characteristics | ✓ | √ | ✓ | ✓ | | |
| C00007 | Baseline characteristics by age group $(\ge 12 \text{ to } < 18, \ge 18 \text{ to } < 65, \ge 65)$ | | | ✓ | ✓ | | |
| Both | Time to last dose/withdrawal from study | ✓ | | | | | |

 $\sqrt{\text{PreD}}$ = Predecessor period only;

 \sqrt{LTE} = LTE period only;

CC

C00007 = D5180C00007;

Rand Teze = Randomised Tezepelumab;

Rand Pbo = Randomised Placebo;

Teze+Teze = Tezepelumab Predecessor+Tezepelumab LTE;

Pbo+Teze = Placebo Predecessor+ Tezepelumab LTE;

Pbo+Pbo = Placebo Predecessor+Placebo LTE;

All Teze = All Tezepelumab;

Table 10 Important PDs, medications, safety and tolerability, and efficacy

| Analysis sets | | SAF | SAF/FAS | | SAF-LTE/FAS-I | CTE CC | CI |
|---------------|---|--------------------------|------------|---------|--------------------------|-----------------------|----|
| Treatmen | nt groups | (Rand Teze/ Rand Pbo) | (All Teze) | ` | ze+Teze/ o+Pbo) | (Pbo+Teze) | |
| Study | Data | Overall | Overall | Overall | By period (PreD, LTE) | By period (PreD, LTE) | |
| Importa | nt protocol deviations (Section 4.2, 4.7.1) | | | | | | |
| Both | Important PDs | | | | √ | ✓ | |
| Prior an | d concomitant medications (Section 4.3) | | | | | | |
| Both | Prior | ✓ | | ✓ | | √Overall | |
| Both | Concomitant (on-treatment) | ✓ | | ✓ | ✓ | √ | |
| Both | Concomitant (post-treatment) | ✓ | | ✓ | | √Overall | |
| Both | Maintenance medications | ✓ | | ✓ | | | |
| Both | Days of systemic corticosteroids | ✓ | | ✓ | √ | √ | |
| C00007 | Total daily OCS dose | ✓ | | ✓ | √ | √ | |
| C00009 | OCS medication at study entry/baseline | ✓ | | ✓ | | | |

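### SAP 3.1.9 does not censor time to premature study withdrawal at the switch to tezepelumab, so the Randomised Placebo withdrawal curve does not follow the group definition in SAP 2.1.2 (minor; descriptive plot only)

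*SAP*

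**What the plan says.** SAP 3.1.9 defines two Kaplan-Meier variables.

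- **Time to last dose of IP.** Placebo subjects who enter the extension and are randomised there to tezepelumab "will be censored on the date of last dose of IP taken from the predecessor study eCRF".
- **Time to premature study withdrawal.** The date comes from the Disposition form. "For subjects enrolling into the LTE study, this will be the Disposition eCRF from the LTE study", with no exception for subjects who change treatment. Subjects still ongoing at the primary database lock are censored at last contact.

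SAP 4.2 places both plots on the safety analysis set and leaves the censoring to that section: "Subjects without the premature event will be censored as described in Section 3.1.9". It does not name the treatment groups for the plots. SAP 8.4, Table 9, does: the row "Time to last dose/withdrawal from study" is ticked only in the safety-set column for Randomised Tezepelumab and Randomised Placebo.

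SAP 2.1.2 defines Randomised Placebo. For subjects who cross over it reads: "Will include all data from first dose/randomisation in predecessor studies up until switch to tezepelumab". Protocol 9.3.1 has the same limit ("predecessor studies up until switch to tezepelumab"). In both documents the group consists of segments D, F, G and H. Segment E, the tezepelumab time of the switchers, is left out.

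**The concern.** SAP 3.1.9 handles the switch for one of its two variables and not for the other. A switcher's follow-up on tezepelumab, and any withdrawal during it, therefore counts in the Randomised Placebo withdrawal curve, although the definition of that group excludes it. Two plots with the same arm label would then describe different populations after roll-over: time to last dose without the switchers, time to withdrawal with them.

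This matters to someone reading the dropout pattern. Protocol 9.3 says that patterns of IP discontinuation will be considered in interpretation. Protocol 9.4.3 allows a different approach to the exacerbation analysis depending on the number and pattern of drop-outs. SAP 4.6.1 treats data missing after study withdrawal as missing at random. A withdrawal plot by arm is a natural place to look for that pattern, and a placebo arm that is partly tezepelumab after roll-over blurs it.

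**Working it through.** The plan states no figure for this point, so there is none to reproduce. The check is a comparison of passages followed by an illustration of size. Year 2 below means roll-over to Week 104.

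**1. Passages side by side**

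| Item | Rule for placebo subjects switched to tezepelumab |
|---|---|
| Group definition (SAP 2.1.2) | Data end at the switch |
| Time to last dose (SAP 3.1.9) | Censored at last predecessor dose |
| Placebo exposure (SAP 3.2.1) | Based on first and last placebo dose |
| Exacerbation time at risk (SAP 3.3.1.1) | Calculated separately by period |
| Time to premature withdrawal (SAP 3.1.9) | Extension Disposition form or last contact; no switch rule |

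Only the last row lacks the switch. No other section supplies a rule for it.

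**2. How many subjects**

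Inputs: 860 and 115 extension enrolees (Protocol 9.2; 860 + 115 = 975, as stated), 90% completing and 90% of those continuing (0.9 × 0.9 = 0.81), and 1:1 re-randomisation of placebo subjects. Protocol 6.3 has: "Subjects previously randomized to blinded placebo will be randomized 1:1 to blinded" tezepelumab or placebo. Equal predecessor arms are implied by the planned 3:1 split: 0.50 + 0.25 = 0.75 on tezepelumab.

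- D5180C00007: 860 / 0.81 = 1062, so 531 per arm. Placebo roll-overs 531 × 0.81 = 430; switchers 430 / 2 = 215. Non-enrolling placebo completers 478 − 430 = 48.
- D5180C00009: 115 / 0.81 = 142, so 71 per arm. Placebo roll-overs 57.5; switchers about 29.

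**3. Effect on the plotted curve**

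The plan's dropout rates are redacted, so Year 2 withdrawal on placebo (p) and tezepelumab (t) is assumed and varied. Study retention at roll-over is assumed to be 90% in both arms, and switchers are assumed to withdraw at rate t.

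- Placebo only: 0.90 × (1 − p)
- As written: 0.90 × (1 − (p + t)/2)

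| p | t | Placebo only | As written |
|---|---|---|---|
| 10% | 5% | 81.0% | 83.25% |
| 15% | 5% | 76.5% | 81.0% |
| 5% | 10% | 85.5% | 83.25% |
| equal | equal | same | same |

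In the first row tezepelumab stands at 0.90 × 0.95 = 85.5%, so the gap between arms reads 85.5 − 83.25 = 2.25 points instead of 85.5 − 81.0 = 4.5. In general the gap is 0.90 × (p − t)/2 instead of 0.90 × (p − t), which is half. Adding the 48 non-enrolling completers of D5180C00007, at risk to Week 64 at the placebo rate, moves the as-written figures in the first two rows only to 83.2% and 80.9%.

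**4. Precision**

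Greenwood standard error at 81% retention, with n subjects per arm and m at risk after roll-over: 0.81 × √(0.1/(0.9n) + 0.1/(0.9m)).

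- D5180C00007 (n = 531): m = 430 gives 1.75 points; m = 215 gives 2.18.
- D5180C00009 (n = 71): m = 57.5 gives 4.79 points; m = 28.75 gives 5.97.

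Both values of m are evaluated at the same retention, to isolate the loss of subjects. The 2.25-point shift is thus about one standard error in D5180C00007 and less than half of one in D5180C00009.

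**The case against.** The best defence is that withdrawal measures follow-up, not exposure, and may reasonably follow the original randomisation to Week 104. Protocol 9.4 describes disposition as running from entry to the predecessor study to the end of the extension. That display is defensible, but the SAP does not say it is intended, and the arm label carries a definition that excludes the switched data.

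It can also be said that SAP 2.1.2 is a general rule which a programmer would apply where a derivation is silent. Section 3.1.9 is not silent, however. It names explicit event and censoring dates for every extension enrolee, and it states the switch rule for the other variable. It is fair that the mismatch depends on one Table 9 row for the treatment groups.

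On size, three criticisms stand. The withdrawal rates are assumed. The 90% is a planning figure that the synopsis words as completing dosing, and subjects who stop IP may still complete the study, so actual study retention could be higher. And the extension disposition table already reports study discontinuation with reasons for "Tezepelumab Predecessor+Tezepelumab LTE, Placebo Predecessor+Placebo LTE and Placebo Predecessor+Tezepelumab LTE".

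A reader might infer more than this:

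- **That the safety or exacerbation results are contaminated.** They are not. The Kaplan-Meier withdrawal time is not an input to either analysis. Adverse events have their own period definitions, and exacerbation time at risk is split by period for cross-over subjects.
- **That the plot flatters one arm.** The documents give no direction. The shift reverses if tezepelumab subjects withdraw more often and vanishes if the rates are equal.

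**Conclusion.** The point holds as a minor inconsistency in one descriptive plot. Applied literally, SAP 3.1.9 leaves subjects assigned to tezepelumab in the Randomised Placebo withdrawal curve, where they make up about half of its extension enrolees. The halving of the Year 2 gap rests on switchers withdrawing like continuing tezepelumab subjects. The point figures rest on assumed rates and assumed 90% retention, and the subject numbers on planned enrolment with equal predecessor arms. No hypothesis is tested (SAP 4.1.1).

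**What to change.** Add one sentence to SAP 3.1.9: placebo subjects randomised to tezepelumab in the extension are censored for time to premature study withdrawal on the date of extension randomisation, whether or not they are dosed.

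The trigger should be randomisation, not first dose. It is the trigger already used for time to last dose, and because the re-randomisation is 1:1 the censoring is non-informative. Receiving a dose is not randomised, and SAP 6 foresees extension subjects who take no IP. Censoring only dosed switchers would keep undosed subjects from both re-randomised arms in a roughly halved risk set. Illustration (assumed): if 1% of the 430 D5180C00007 placebo roll-overs withdraw undosed, 4.3 events would fall on about 217 at risk, or 2.0% instead of 1.0%.

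Two alternatives also work:

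- plot the extension period separately for the three groups of the extension disposition table; or
- if follow-up by original randomisation is intended, say so and label the curve as including subjects switched to tezepelumab.

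The cost is one sentence and one derivation. No period date, adverse event rate or exacerbation offset changes. The downside is precision: the Year 2 placebo curve rests on about half the subjects, so the standard error of Week 104 retention becomes about 2.2 instead of 1.8 points in D5180C00007 and 6.0 instead of 4.8 in D5180C00009, under the assumptions above.
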